8.1.3 Vital signs

- For timings of assessments refer to the study plans in Table 1 (Screening and the Treatment Period).
- Patients will be monitored with assessment of vital signs (BP, pulse, respiratory rate, temperature and oxygen saturation) at Screening and on the day of each infusion and in the follow-up period. On infusion days vital signs will all be taken before the infusion.
- Additional monitoring with assessment of vital signs is at the discretion of the Investigator per standard clinical practice or as clinically indicated.
- Additional recording of vital signs may be captured on an unscheduled vital signs eCRF and on the eCRF for AE/SAE where applicable. The date and time of collection and measurement will be recorded on the appropriate eCRF.
- The date and time of collection and measurement will be recorded on the appropriate eCRF.
- Temperature, respiratory rate and oxygen saturation: On infusion days, temperature, respiratory rate and oxygen saturation should be collected before the infusion.

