8.2.6 Adverse events based on examinations and tests

The results from the Clinical Study Protocol mandated laboratory tests and vital signs will be summarised in the CSR. Deterioration as compared to baseline in protocol-mandated laboratory values, vital signs should therefore only be reported as AEs if they fulfil any of the SAE criteria or are the reason for discontinuation of treatment with the investigational product.

If deterioration in a laboratory value/vital sign is associated with clinical signs and symptoms, the sign or symptom will be reported as an AE and the associated laboratory result/vital sign will be considered as additional information. Wherever possible the reporting Investigator uses the clinical, rather than the laboratory term (e.g., anaemia versus low haemoglobin value). In the absence of clinical signs or symptoms, clinically relevant deteriorations in non-mandated parameters should be reported as AE(s).

Deterioration of a laboratory value, which is unequivocally due to disease progression, should not be reported as an AE/SAE.

Any new or aggravated clinically relevant abnormal medical finding at a physical examination as compared with the baseline assessment will be reported as an AE unless unequivocally related to the disease under study, see sections 8.3.9 and 8.310.

Disease progression can be considered as a worsening of a patient's condition attributable to the disease for which the investigational product is being studied. It may be an increase in the severity of the disease under study and/or increases in the symptoms of the disease. The development of new, or progression of existing metastasis to the primary cancer under study should be considered as disease progression and not an AE. Events, which are unequivocally due to disease progression, should not be reported as an AE during the study.

New cancers

The development of a new cancer should be regarded as an SAE. New primary cancers are those that are not the primary reason for the administration of the study drug and have been identified after the patient's inclusion in this study.

Deaths

All deaths that occur during the study, or within the protocol-defined follow-up period after the administration of the last dose of study drug, must be reported as follows:

- Death clearly the result of disease progression should be reported to the study monitor at the next monitoring visit and should be documented in the eCRF but should not be reported as a SAE.

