6.3.1 Primary Endpoint Analysis

The primary analysis for primary endpoint will be based on Safety Analysis Set.

Primary Endpoint evaluations will include Adverse Events (AEs), Serious Adverse Events (SAEs), Adverse Events of Special Interest (AESI) including interstitial lung disease/pneumonitis-like events and on study Deaths.

Adverse Events (AEs), Serious Adverse Events (SAEs), Adverse Events of Special Interest (AESI) including interstitial lung disease/pneumonitis-like events and on study Deaths will be summarized using Frequency, Percentages.

Physical Examination will include General Appearance, Respiratory system, Cardiovascular system, Abdomen, Skin, Heent, Neck, Lymph node, Thyroid, Musculo-skeletal system, Genital/Rectal and Neurological System. Physical Examination will be summarized based on the Safety Analysis Set.

Descriptive summaries will be provided for the Physical Examination.

Document Title:	Document ID:	BP04-01
Statistical Analysis Plan	Version Number:	3.1
	Effective Date:	25-Nov-2021

All the continuous variables will be summarized by n, mean, standard deviation, minimum, median and maximum values. All the categorical variables will be summarized as frequency, percentage.

Vital Signs will include Pulse rate, Respiratory rate, Systolic Blood Pressure, Diastolic Blood Pressure, Oxygen Saturation and Temperature. Vital Signs will be summarized based on the Safety Analysis Set.

Vital Signs will be summarised by number of observations, arithmetic mean, SD, median, minimum and maximum values.

12-Lead Electrocardiogram will include Heart rate, QRS, PR, RR, QT and QTcF. 12-Lead Electrocardiogram will be summarized based on the Safety Analysis Set.

12-Lead Electrocardiogram will be summarised by number of observations, arithmetic mean, SD, median, minimum and maximum values.

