- The Capital "N" in the column header represents the total number Safety Analysis Set.
- The small "n" represents the total number of patients in the row category.
- All Percentages rows are based on number of Safety Analysis Set.
- Programmer Note: Visit x Visit 1 up to Visit 12.
- Source: Listing 16.3.2

Document Title:	Document ID:	BP04-01
Statistical Analysis Plan	Version Number:	3.1
	Effective Date:	25-Nov-2021

Table 14.3.2 Summary of Vital Sign (Safety Analysis Set)

	N = xx
Visit x	
Examination Done, n (%)	
Yes	xx (xx.xx)
No	xx (xx.xx)
Missing	xx (xx.xx)
Systolic Blood Pressure (mmHg)	
n	Xx
Missing	Xx
Mean (SD)	xx.x (xx.xx)
Median	xx.x
(min, max)	(xx.xx, xx.xx)
Diastolic Blood Pressure (mmHg)	
n	Xx
Missing	Xx
Mean (SD)	xx.x (xx.xx)
Median	xx.x
(min, max)	(xx.xx, xx.xx)
Pulse Rate (beats/min)	
n	Xx
Missing	Xx
Mean (SD)	xx.x (xx.xx)
Median	xx.x
(min, max)	(xx.xx, xx.xx)
Respiratory Rate (breaths/min)	
n	Xx
Missing	Xx
Mean (SD)	xx.x (xx.xx)
Median	xx.x
(min, max)	(xx.xx, xx.xx)
Temperature (°F)	
n	Xx
Missing	Xx
Mean (SD)	xx.x (xx.xx)
Median	xx.x
(min, max)	(xx.xx, xx.xx)
Oxygen Saturation (%)	
n	Xx
Missing	Xx
Mean (SD)	xx.x (xx.xx)
Median	xx.x
(min, max)	(xx.xx, xx.xx)
Weight (Kg)	
n	Xx
Missing	Xx

Page 39 of 77

Proprietary and Confidential Document

Document Title:	Document ID:	BP04-01
Statistical Applicate Plans	Version Number:	3.1
Statistical Analysis Plan	Effective Date:	25-Nov-2021

 Mean (SD)
 xx.x (xx.xx)

 Median
 xx.x

 (min, max)
 (xx.xx, xx.xx)

- The Capital "N" in the column header represents the total number Safety Analysis Set.
- The small "n" represents the total number of patients in the row category.
- Percentages in the "Examination Done" rows are based on number of Safety Analysis Set.
- SD = Standard Deviation, min=minimum, max=maximum
- Programmer Note: Visit x Visit 2 up to Visit 12.
- Source: Listing 16.3.3

Document Title:	Document ID:	BP04-01
Statistical Analysis Plan	Version Number:	3.1
	Effective Date:	25-Nov-2021

Table 14.3.3 Summary of 12-Lead Electrocardiogram (Safety Analysis Set)

	N = xx
Visit x	
Assessment Done, n (%)	
Yes	xx (xx.xx)
No	xx (xx.xx)
Missing	xx (xx.xx)
Heart rate (beats/min)	
n	Xx
Missing	Xx
Mean (SD)	xx.x (xx.xx)
Median	xx.x
(min, max)	(xx.xx, xx.xx)
QRS (ms)	
n	Xx
Missing	Xx
Mean (SD)	xx.x (xx.xx)
Median	XX.X
(min, max)	(xx.xx, xx.xx)
PR (ms)	
n	Xx
Missing	Xx
Mean (SD)	xx.x (xx.xx)
Median	xx.x
(min, max)	(xx.xx, xx.xx)
RR (ms)	
n	Xx
Missing	Xx
Mean (SD)	xx.x (xx.xx)
Median	xx.x

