xxxxxx	Yes/No	XXX	XXX	xxx	XXX	DD-MMM-YYYY/HH:MM	DD-MMM-YYYY/HH:MM	XX	xxx
XXXXXX	Yes/No	XXX	XXX	xxx	XXX	DD-MMM-YYYY/HH:MM	DD-MMM-YYYY/HH:MM	XX	xxx
XXXXXX	Yes/No	XXX	xxx	xxx	xxx	DD-MMM-YYYY/HH:MM	DD-MMM-YYYY/HH:MM	xx	xxx

Document Title:	Document ID:	BP04-01
Statistical Analysis Plan	Version Number:	3.1
	Effective Date:	25-Nov-2021

Listing 16.3.1.3 Listing of Patient Adverse Event

Unique	Adverse	AE No.	Adverse Event	Treatment	Relationship	Outcome	Serious AE	Therapy
Patient	Event		Term	given	with study Drug			Discontinued
ID								
XXXXXXX	Yes/No	XXX	XXX	Yes/No	XXX	XXX	Yes/No	Yes/No
XXXXXXX	Yes/No	XXX	XXX	Yes/No	XXX	XXX	Yes/No	Yes/No
XXXXXXX	Yes/No	XXX	XXX	Yes/No	XXX	XXX	Yes/No	Yes/No
XXXXXX	Yes/No	XXX	XXX	Yes/No	XXX	XXX	Yes/No	Yes/No
XXXXXX	Yes/No	XXX	xxx	Yes/No	XXX	XXX	Yes/No	Yes/No

Document Title:	Document ID:	BP04-01
Statistical Analysis Plan	Version Number:	3.1
	Effective Date:	25-Nov-2021

Listing 16.3.2 Listing of Patient Physical Examination

Unique Patient ID	Visit	Examination done	Date and Time of Assessment	Physical Examination	Result	If Abnormal
XXXXXX	XXX	Yes/No	DD-MMM-YYYY/HH:MM	XXX	Normal/Abnormal	CS/NCS
XXXXXX	XXX	Yes/No	DD-MMM-YYYY/HH:MM	XXX	Normal/Abnormal	CS/NCS
XXXXXX	XXX	Yes/No	DD-MMM-YYYY/HH:MM	XXX	Normal/Abnormal	CS/NCS
XXXXXX	XXX	Yes/No	DD-MMM-YYYY/HH:MM	xxx	Normal/Abnormal	CS/NCS
XXXXXX	XXX	Yes/No	DD-MMM-YYYY/HH:MM	xxx	Normal/Abnormal	CS/NCS

Document Title:	Document ID:	BP04-01
Statistical Analysis Plan	Version Number:	3.1
	Effective Date:	25-Nov-2021

Listing 16.3.3 Listing of Patient Vital Signs

Unique Patient	Visit	Examination Done	Date and Time of Assessment	Parameter	Result	Assessment Result	If Abnormal
ID							
XXXXXXX	XXX	Yes/No	DD-MMM-YYYY/HH:MM	XXX	xxx	Normal/Abnormal	xxx
XXXXXXX	XXX	Yes/No	DD-MMM-YYYY/HH:MM	XXX	XXX	Normal/Abnormal	xxx
XXXXXXX	XXX	Yes/No	DD-MMM-YYYY/HH:MM	XXX	XXX	Normal/Abnormal	XXX
XXXXXX	XXX	Yes/No	DD-MMM-YYYY/HH:MM	XXX	xxx	Normal/Abnormal	XXX
XXXXXX	XXX	Yes/No	DD-MMM-YYYY/HH:MM	XXX	xxx	Normal/Abnormal	XXX

Document Title:	Document ID:	BP04-01
Statistical Analysis Plan	Version Number:	3.1
	Effective Date:	25-Nov-2021

Listing 16.3.4 Listing of Patient 12-Lead electrocardiogram

Unique		Assessment	Date and Time of ECG				
Patient ID	Visit	Done	assessment	Parameter	Result	Unit	Interpretation
xxxxxx	XXX	Yes/No	DD-MMM-YYYY/HH:MM	XXX	XXX	XXX	xxx
XXXXXX	XXX	Yes/No	DD-MMM-YYYY/HH:MM	XXX	XXX	XXX	XXX
XXXXXXX	XXX	Yes/No	DD-MMM-YYYY/HH:MM	XXX	XXX	XXX	XXX
XXXXXX	XXX	Yes/No	DD-MMM-YYYY/HH:MM	XXX	XXX	XXX	XXX

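### Vital-sign deterioration that Protocol 8.2.6 leaves to the CSR summary is not counted in any SAP table, because Table 14.3.2 makes no comparison with baseline

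*SAP*

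**What the plan says.** Protocol 8.2.6 states that mandated laboratory and vital-sign results will be summarised in the CSR, and draws a reporting rule from that: "Deterioration as compared to baseline in protocol-mandated laboratory values, vital signs should therefore only be reported as AEs if they fulfil" a seriousness criterion or are the reason for stopping the investigational product. The next paragraph adds an exception: where deterioration comes with clinical signs or symptoms, the sign or symptom is reported as an AE.

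SAP 6.3.1 names the parameters: "Vital Signs will include Pulse rate, Respiratory rate, Systolic Blood Pressure, Diastolic Blood Pressure, Oxygen Saturation and Temperature". It then gives the summary: "Vital Signs will be summarised by number of observations, arithmetic mean, SD, median, minimum and maximum values". The shell of Table 14.3.2 (SAP section 8) lays this out visit by visit for Visits 2 to 12, with a count of missing values for each parameter. It has no rows for change, shift, worst value or number of patients affected, and no baseline is defined for vital signs.

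Listing 16.3.3 shows each patient's result by visit and parameter, with a Normal/Abnormal column headed "Assessment Result". No table counts that column. Protocol 8.1.3 also allows for extra readings: "Additional recording of vital signs may be captured on an unscheduled vital signs eCRF". The programmer note to Table 14.3.2 covers the numbered visits only.

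**The concern.** The two documents do not meet. The protocol sets one kind of deterioration aside from AE reporting, defines it by comparison with baseline, and relies on the CSR summary to show it. The planned summary makes no such comparison.

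Safety is the trial's only objective, and events resembling interstitial lung disease or pneumonitis are the named events of special interest, so oxygen saturation is one of the vital signs a reader will look at. A fall that is non-serious, without symptoms and not the cause of stopping reaches the CSR only through a by-visit distribution and a listing. At stake is whether the report can say how many patients deteriorated and by how much.

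**Working it through.** The plan states no figure on this point, so there is none to reproduce. The check sets the texts side by side and then illustrates what the planned statistics can show.

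**1. What 8.2.6 leaves to the summary.**

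| Vital-sign deterioration | Where it is counted |
|---|---|
| Meets a seriousness criterion | AE tables |
| Is the reason for stopping treatment | AE tables, including Table 14.2.1.5 |
| Comes with signs or symptoms | AE tables, as the sign or symptom |
| None of these | CSR vital-sign summary only |

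Only the last row is at issue.

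**2. What other SAP tables do.** Tables 14.3.1 (physical examination) and 14.3.4.1 to 14.3.4.4 (laboratory) count patients Normal or Abnormal, and split the abnormal by clinical significance. Table 14.1.8 counts patients whose performance grade changed since the last visit. Vital signs have a Normal/Abnormal field, but it is only listed.

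**3. Size of the listing.** With 100 patients, 11 visits (2 to 12) and 6 parameters, it can run to 100 × 11 × 6 = 6,600 rows.

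**4. What one visit's row can show.** The document input is about 100 patients. The rest is assumed: true oxygen saturation with mean 96.5 and SD 1.2, visit-to-visit noise with SD 0.9, and k patients who fall D points and still attend.

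- Observed SD with no falls: √(1.2² + 0.9²) = √2.25 = 1.5.
- Shift in the visit mean: −kD/100.
- Visit SD with falls, before rounding and the cap at 100: √(2.25 + p(1 − p)D²), where p = k/100. For k = 10 and D = 6 this is √(2.25 + 0.09 × 36) = √5.49 = 2.34.
- Average minimum, and average number of patients with a within-patient change of −4 or lower: simulation, 4,000 replicates, values rounded to whole points and capped at 100.

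| k | D | Mean shift | SD | Minimum | Patients with change ≤ −4 |
|---|---|---|---|---|---|
| 5 | 4 | −0.2 | 1.73 | 90.7 | 3.5 |
| 10 | 4 | −0.4 | 1.92 | 90.2 | 6.8 |
| 15 | 4 | −0.6 | 2.07 | 89.9 | 10.0 |
| 5 | 6 | −0.3 | 1.99 | 88.8 | 5.2 |
| 10 | 6 | −0.6 | 2.34 | 88.2 | 10.1 |
| 15 | 6 | −0.9 | 2.62 | 87.9 | 14.9 |

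With no falls the minimum averages about 92.7. The last column includes about 0.3 patients by chance. The 4-point cut is for illustration and is not a proposed clinical threshold.

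The planned statistics do react: the minimum drops and the SD widens. They do not separate number from size. A mean shift of −0.6 arises from 15 falls of 4 points or from 10 falls of 6. The SD is close to 1.9 or 2.0 with 10 falls of 4 or 5 falls of 6. Within-patient change gives the number directly, although noise hides some falls close to the cut.

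**The case against.** The strongest reply is that this is presentation. The endpoint is AEs, serious AEs, events of special interest and deaths. Vital signs are supportive description in a single-arm study that tests no hypothesis, and every value is listed with its assessment. That is fair, and it is why the point is minor. It does not close the gap, because 8.2.6 assigns these events to a summary and a listing is not one.

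A reader might infer more than the documents support:

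- **That vital signs are summarised by means alone, or that deterioration cannot be seen.** SD, median, minimum, maximum, number observed and number missing are also planned, and Listing 16.3.3 shows each patient's values. The deterioration is uncounted, not hidden.
- **That 8.2.6 suppresses all deterioration.** Serious events, events that stop treatment, and accompanying signs or symptoms are all reported.
- **That oxygen saturation is the only scheduled objective respiratory measure.** Respiratory rate is in the same table. Respiratory examination is scheduled at Visits 1, 2 and 12, symptom-targeted in between, and tabulated in Table 14.3.1. Pneumonitis itself is recorded as an AE diagnosis, so that endpoint does not depend on Table 14.3.2.
- **That the main loss is patients who fall and then leave.** If the fall caused the stop, it is an AE. In addition, the synopsis treats an early stopper's last visit as the End-of-Evaluation visit, so some of those values may appear under Visit 12. Mixing them with Day 141 values is a further reason to compare each patient with baseline.

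**Conclusion.** The point holds in a narrow form. Non-serious, asymptomatic vital-sign deterioration from baseline that does not lead to stopping treatment is excluded from AE reporting on the strength of a CSR summary, and the SAP summary neither compares with baseline nor counts patients. This rests on the text of Protocol 8.2.6, SAP 6.3.1, Table 14.3.2 and Listing 16.3.3, and needs no assumption.

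The size is illustrative only. Under the assumed saturation values, 5 to 15 affected patients in 100 move a visit mean by 0.2 to 0.9 points, and the other planned statistics signal an extreme without saying how many patients it represents. The documents give no expected number of such patients. The primary endpoint is unaffected. This is an inexpensive improvement, not a flaw that threatens the trial.

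**What to change.** Before database lock, amend SAP 6.3.1 and Table 14.3.2:

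1. Define vital-sign baseline as the last value before the first infusion (Visit 2). State that it is pre-infusion, because the Schedule of Activities mentions readings before and after infusion while Protocol 8.1.3 places them before.
2. For each parameter and visit, add change from baseline in patients with both values.
3. Add n (%) of patients with at least one Abnormal assessment after the first dose, using the field already in Listing 16.3.3. Include unscheduled readings where that assessment was recorded; the documents do not say that it always will be.
4. Summarise the distribution of each patient's largest fall in oxygen saturation from baseline. A note should say that a maximum over repeated visits picks up some noise: in the illustration, 0.3 chance falls of 4 points or more per visit become at most about 3 per 100 patients over Visits 3 to 12 (10 × 0.3).

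No clinical threshold is needed. If the sponsor wants one, it should be set in advance. The cost is a few extra rows in one table, from scheduled data already collected.

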- The Capital "N" in the column header represents the total number of patients in Enrolled Analysis Set.
- The small "n" in summary statistics represents the total number of patients in the row category.
- Percentages are based on the total number patients in Enrolled Analysis Set.
- Enrolled Analysis Set: The enrolled population is defined as all screened patients who provided written informed consent at screening assessment, satisfied all the eligibility criteria and enrolled into the study.
- Safety Population: All the patients who are enrolled into the study and received at least one dose of investigational product as an IV infusion.

Source: Listing 16.1.1.4
 Table Name: xxxxxxxx

Document Title:	Document ID:	BP04-01
Statistical Analysis Plan	Version Number:	3.1
	Effective Date:	25-Nov-2021

Table 14.1.1.3 Summary of Protocol Deviation (Enrolled Analysis Set)

	Durvalumab
	N = xxx
	n (%)
Patient undergone any Protocol Deviation	
Yes	xx (xx.xx)
No	xx (xx.xx)
Protocol Deviation	
Restrictions	xx (xx.xx)
Enrolment/IE Criteria	xx (xx.xx)
Out of visit window	xx (xx.xx)
IP Administration	xx (xx.xx)
Drug accountability	xx (xx.xx)
Noncompliance	xx (xx.xx)
Use of prohibited medication	xx (xx.xx)
Safety assessment	xx (xx.xx)
Other	xx (xx.xx)
Other 1	xx (xx.xx)
Other n	xx (xx.xx)
Action Taken	
Patient continued in the study	xx (xx.xx)
Patient Discontinued in the study	xx (xx.xx)
Retraining	xx (xx.xx)
Other	xx (xx.xx)
Other 1	xx (xx.xx)
Other n	xx (xx.xx)

- The Capital "N" in the column header represents the total number of patients in Enrolled Analysis Set.
- The small "n" represents the total number of patients in the row category.
- Percentages are based on number of patients in Enrolled Analysis Set.
- Patients may have more than one protocol deviation.
- Source: Listing 16.1.1.3

Document Title:	Document ID:	BP04-01
Statistical Analysis Plan	Version Number:	3.1
	Effective Date:	25-Nov-2021

Table 14.1.2 Summary of Demographic and Baseline Characteristics (Enrolled Analysis Set)

Demographic and Baseline Variables	N = xx
Age (Years)	
n	Xx
Missing	Xx
Mean (SD)	xx.x (xx.xx)
Median	xx.x
(min, max)	(xx.xx, xx.xx)
Gender, n (%)	
Male	xx (xx.xx)
Female	xx (xx.xx)
Missing	xx (xx.xx)
Height (cm)	
N	Xx
Missing	Xx
Mean (SD)	xx.x (xx.xx)
Median	xx.x
(min, max)	(xx.xx, xx.xx)
Weight (Kg)	
n	Xx
Missing	Xx
Mean (SD)	xx.x (xx.xx)
Median	xx.x
(min, max)	(xx.xx, xx.xx)
Race, n (%)	
Indian	xx (xx.xx)
Other	xx (xx.xx)
Other 1	xx (xx.xx)
Other n	xx (xx.xx)

- The Capital "N" in the column header represents the total number of patients in Enrolled Analysis Set.
- The small "n" in summary statistics represents the total number of patients.
- Percentages are based on number of patients in Enrolled Analysis Set.
- SD = Standard Deviation, min=minimum, max=maximum
- Source: Listing 16.1.2

Document Title:	Document ID:	BP04-01
Statistical Analysis Plan	Version Number:	3.1
	Effective Date:	25-Nov-2021

Table 14.1.3 Summary of Significant Medical/Surgical History (Enrolled Analysis Set)

System Organ Class Preferred Term	Durvalumab N = xx n (%)
Number of patient with at least one medical/Surgical history	xx (xx.xx)
System Organ Class 1	xx (xx.xx)
Preferred Term 1	xx (xx.xx)
Preferred Term 2	xx (xx.xx)
System Organ Class 2	xx (xx.xx)
Preferred Term 1	xx (xx.xx)
Preferred Term 2	xx (xx.xx)
System Organ Class 3	xx (xx.xx)
Preferred Term 1	xx (xx.xx)
Preferred Term 2	xx (xx.xx)

- The Capital "N" in the column header represents the total number of patients in Enrolled Analysis Set.
- The small "n" in summary statistic represents the total number of patients in the row category.
- Percentages are based on number of patients in Enrolled Analysis Set.
- System Organ Class and Preferred term are coded using standards of MedDRA version xx.x
- Patient having a medical history of similar SOC/PT more than once will be counted only once.
- Source: Listing 16.1.3
- Table Name: xxxx
- Programmer's Note 1: The above table will be continued for all other SOC and PT terms.
- Programmers Note 2: SOC and PT will be sorted in descending order of frequency.

Document Title:	Document ID:	BP04-01
Statistical Analysis Plan	Version Number:	3.1
	Effective Date:	25-Nov-2021

Table 14.1.4.1 Summary of Alcohol consumption and drug abuse (Enrolled Analysis Set)

	Durvalumab N = xx
	n (%)
lumber of patients with significant history of alcoholism or drug abuse	xx (xx.xx)
Alcohol	
Current	xx (xx.xx)
Past	xx (xx.xx)
Never	xx (xx.xx)
Drug	
Current	xx (xx.xx)
Past	xx (xx.xx)
Never	xx (xx.xx)

- The Capital "N" in the column header represents the total number of patients in Enrolled Analysis Set.
- The small "n" in summary statistic represents the total number of patients in the row category.
- =Percentages are based on total number of patients in Enrolled Analysis Set.
- Source: Listing 16.1.6.1
- Table number: xxxxx

Document Title:	Document ID:	BP04-01
Statistical Analysis Plan	Version Number:	3.1
Statistical Analysis Plan	Effective Date:	25-Nov-2021

Table 14.1.4.2 Summary of History of Tobacco (Enrolled Analysis Set)

	Durvalumab
	N = xxx
	n (%)
Smoking History	
Current	xx (xx.xx)
Past	xx (xx.xx)
Never	xx (xx.xx)

- The Capital "N" in the column header represents the total number of patients in Enrolled Analysis Set.
- The small "n" in summary statistic represents the total number of patients in the row category.
- Percentages are based on total number of patients in Enrolled Analysis Set.
- Source: Listing 16.1.6.2
- Table Name: xxxxx

Document Title:	Document ID:	BP04-01
Statistical Analysis Plan	Version Number:	3.1
Statistical Analysis Plan	Effective Date:	25-Nov-2021

Table 14.1.5.1 Summary of IP Administration (Enrolled Analysis Set)

	Durvalumab
	N = xx
Visit 2	
Total Dose Administered(mg/mL)	
n	Xx
Missing	Xx
Mean (SD)	xx.x (xx.xx)
Median	xx.x
(min, max)	(xx.xx, xx.xx)
Dose interrupted during infusion, n (%)	
No	xx (xx.xx)
Yes	xx (xx.xx)
Dose Restarted, n (%)	
Yes	xx (xx.xx)
No	xx (xx.xx)

- The Capital "N" in the column header represents the total number of patients in Enrolled Analysis Set.
- The small "n" in summary statistic represents the total number of patients in the row category.
- Percentages are based on number of patients in Enrolled Analysis Set.
- SD = Standard Deviation, min=minimum, max=maximum
- Source: Listing 16.1.4.1 and Listing 16.1.4.2
- Table Name: xxxxx
- Programmer Note: Continue the above table from Visit 2 to Visit 11.

Document Title:	Document ID:	BP04-01
Statistical Analysis Plan	Version Number:	3.1
	Effective Date:	25-Nov-2021

Table 14.1.5.2 Summary of Study drug Administration accountability (Enrolled Analysis Set)

	N = xx
At Visit 11,	
Dose Reduced in any of the Visit , n (%)	
Yes	xx (xx.xx)
No	xx (xx.xx)
Dosing Completed, n (%)	
Yes	xx (xx.xx)
No	xx (xx.xx)
Number of IV Dose administered in the treatment period	
n	Xx
Missing	Xx
Mean (SD)	xx.x (xx.xx)
Median	xx.x
(min, max)	(xx.xx, xx.xx)
Unused IP returned, n (%)	
Yes	xx (xx.xx)
No	xx (xx.xx)
Compliance (%)	
n	Xx
Missing	Xx
Mean (SD)	xx.x (xx.xx)
Median	xx.x
(min, max)	(xx.xx, xx.xx)

- The Capital "N" in the column header represents the total number of patients in Enrolled Analysis Set.
- The small "n" represents the total number of patients in the row category.
- All Percentages rows are based on number of patients in Enrolled Analysis Set.
- SD = Standard Deviation, min=minimum, max=maximum
- Source: Listing 16.1.4.3
- Table Name: xxxxx

Document Title:	Document ID:	BP04-01
Statistical Analysis Plan	Version Number:	3.1
Statistical Analysis Plan	Effective Date:	25-Nov-2021

Table 14.1.6 Summary of Disease Characteristics Assessment (Enrolled Analysis Set)

	Durvalumab
	N = xx
	n (%)
At Visit x	
Disease Stage of NSCLC	
Stage IIIA	xx (xx.xx)
Stage IIIB	xx (xx.xx)
Stage IIIC	xx (xx.xx)

- The Capital "N" in the column header represents the total number of patients in Enrolled Analysis Set.
- The small "n" in summary statistic represents the total number of patients in the row category.
- Percentages are based on total number of patients in Enrolled Analysis Set.
- Programmer Note:- Visit x : Visit 2, Visit 5, Visit 8, Visit 11 and Visit 12.
- Source: Listing 16.1.5
- Table Name: xxxx

Document Title:	Document ID:	BP04-01
Statistical Analysis Diam	Version Number:	3.1
Statistical Analysis Plan	Effective Date:	25-Nov-2021

Table 14.1.7 Summary of Radiation Treatment (Enrolled Analysis Set)

	N = xx
Clinical Stage of NSCLC	
Stage IIIA	xx (xx.xx)
Stage IIIB	xx (xx.xx)
Stage IIIC	xx (xx.xx)
Pathological staging of NSCLC done	
No	xx (xx.xx)
Yes	xx (xx.xx)
Stage IIIA	xx (xx.xx)
Stage IIIB	xx (xx.xx)
Stage IIIC	xx (xx.xx)
Histology of Tumor	
Squamous	xx (xx.xx)
Non-squamous	xx (xx.xx)
Technique of Radiation	
Sequential Communication of the Communication of th	
IMRT .	xx (xx.xx)
IGRT CONTROL OF THE PROPERTY O	xx (xx.xx)
Proton	xx (xx.xx)
SBRT	xx (xx.xx)
Other Other	xx (xx.xx)
Other 1	xx (xx.xx)
Other 2	xx (xx.xx)
Concurrent	
IMRT	xx (xx.xx)
IGRT	xx (xx.xx)
Proton	xx (xx.xx)
SBRT	xx (xx.xx)
Other	xx (xx.xx)
Other 1	xx (xx.xx)
Other 2	xx (xx.xx)
Dose of Radiation (Gy)	
n	Xx
Missing	Xx
Mean (SD)	xx.x (xx.xx)
Median	XX.X
(min, max)	(xx.xx, xx.xx)
nduction chemotherapy given	, ,
Yes	xx (xx.xx)
No	xx (xx.xx)
If Yes, Number of cycles	, -7
n	Xx

Proprietary and Confidential Document

Page 25 of 77

Document Title:	Document ID:	BP04-01
Statistical Analysis Plan	Version Number:	3.1
	Effective Date:	25-Nov-2021

Mean (SD) XX.X (XX.XXX) Median (min, max) (XX.X (XX.XXX) Type of Chemotherapy Sequential Concurrent Number of cycles (Sequential) n XX Missing XX Mean (SD) XX.X (XX.XXX) Median (min, max) (XX.XX, XX.XXXX) Number of cycles (Concurrent) XX n XX Missing XX Mean (SD) XX.X (XX.XXX) Median (XXX, XX.XXXXXXXXXXXXXXXXXXXXXXXXXXXXXX		
(min, max) (xxxxx, xxxxxx) Type of Chemotherapy Sequential Concurrent Xx Number of cycles (Sequential) Xx n Xx Mean (SD) xxxx (xxxxx) Median (xxxxx) (min, max) (xxxxx, xxxxxxxxxxxxxxxxxxxxxxxxxxxxxxx	Mean (SD)	xx.x (xx.xx)
Type of Chemotherapy Sequential Concurrent Number of cycles (Sequential) Xx n Xx Missing Xx Mean (SD) xx.x Median (xx.xx) Number of cycles (Concurrent) Xx n Xx Missing Xx Mean (SD) xx.x Median xx.x xx.x xx.x Median xx.x xx.x xx.x xx.x xx.x xx.x xx.x xx.x xx.x xx.x xx.x xx.x xx.x xx.x xx.x xx.x Median	xx.x	Median	xx.x
Sequential Concurrent Number of cycles (Sequential) n Xx Missing Xx Mean (SD) xx.x (xx.xx) Median xx.x (min, max) (xx.xx, xx.xx) Number of cycles (Concurrent) Xx n Xx Mesning Xx Mean (SD) xx.x (xx.xx) Median xx.x (min, max) (xx.xx, xx.xx) Mean (SD) xx.x (xx.xxx) Median xx.x (min, max) (xx.xx, xx.xxx) Performance status at time of initiation of CRT xx n Xx Missing Xx Mean (SD) xx.x (xx.xxxx) Median xx.x (xin, max) xx.x (xx.xxxxxxxxxxxxxxxxxxxxxxxxxxxxxx	(min, max)	(xx.xx, xx.xx)
Concurrent Number of cycles (Sequential) n Xx Missing Xx Mean (SD) XX. (XX.XX) Median XX.X (min, max) (XX.XX) Number of cycles (Concurrent) XX n XX Missing XX Median XX.X (min, max) (XX.XX) Tumor response assessment done on imaging (days) XX n XX Missing XX Median XX.X (min, max) (XX.XXX) Performance status at time of initiation of CRT XX n XX Missing XX Missing XX Missing XX Mean (SD) XX Median XX	Type of Chemotherapy	
Number of cycles (Sequential) Xx n Xx Missing Xx Mean (SD) XX.X (XX.XX) Median XX.X (min, max) (XX.XX, XX.XX) Number of cycles (Concurrent) XX n XX Missing XX Median XX.X (min, max) (XX.XX, XX.XX) Tumor response assessment done on imaging (days) XX n XX Missing XX Median XX.X (min, max) (XX.XX, XX.XX) Performance status at time of initiation of CRT XX n XX Missing XX Mean (SD) XX.X Mean (SD) XX.X Mean (SD) XX.X Median XX.X Median XX.X Median XX.X (min, max) (XX.XX, XX.XX)	Sequential	
n Xx Missing Xx Mean (SD) xx.x (xx.xx) Median xx.x (min, max) (xx.xx, xx.xx) Number of cycles (Concurrent) Xx n Xx Missing Xx Mean (SD) xx.x (xx.xx) Median (xx.xx, xx.xx) Tumor response assessment done on imaging (days) Xx n Xx Missing Xx Mean (SD) xx.x (xx.xx) Median xx.x (min, max) (xx.xx, xx.xx) Performance status at time of initiation of CRT Xx Missing Xx Mean (SD) xx.x (xx.xx) Median xx.x (xx.xx) Median xx.x (xx.xx) Median xx.x (xx.xx)	Concurrent	
Missing Mean (SD) XX Median (SD) XX.X (min, max) (XX.XX, XX.XX) Number of cycles (Concurrent) n XX Missing XX Mean (SD) XX.X Median XX.X (min, max) (XX.XX, XX.XX) Tumor response assessment done on imaging (days) XX n XX Missing XX Mean (SD) XX.X (XX.XX) Median XX.X (min, max) (XX.XX, XX.XX) Performance status at time of initiation of CRT XX Missing XX Mean (SD) XX Mean (SD) XX Mean (SD) XX Median XX Median XXX Median XXX Median XXX	Number of cycles (Sequential)	
Mean (SD) xx.x (xx.xx) Median xx.x (min, max) (xx.xx, xx.xx) Number of cycles (Concurrent) Xx n Xx Missing Xx Mean (SD) xx.x (xx.xx) Median (xx.xx, xx.xx) Median (xx.xx, xx.xx) In Xx Missing Xx Mean (SD) xx.x (xx.xx) Median xx.x (min, max) (xx.xx, xx.xx) Performance status at time of initiation of CRT Xx n Xx Missing Xx Missing Xx Mean (SD) xx.x (xx.xx) Mean (SD) xx.x (xx.xx) Median xx.x (xx.xx) Median xx.x (xx.xx)	n	Xx
Median (min, max) xxxx Number of cycles (Concurrent) Xx n Xx Missing Xx Mean (SD) xxx.x (xx.xx) Median xx.x (min, max) (xx.xx, xx.xx) Tumor response assessment done on imaging (days) Xx n Xx Missing Xx Mean (SD) xx.x (xx.xx) Median xx.x (min, max) (xx.xx, xx.xx) Performance status at time of initiation of CRT Xx Missing Xx Mean (SD) xx.x (xx.xx) Median xx.x (xx.xx) xx.x Median xx.x (min, max) (xx.xx, xx.xx)	Missing	Xx
(min, max) (xx.xx, xx.xx) Number of cycles (Concurrent) Xx n Xx Missing Xx Mean (SD) xx.x (xx.xx) Median xx.x (min, max) (xx.xx, xx.xx) Tumor response assessment done on imaging (days) Xx n Xx Missing Xx Median (SD) xx.x (xx.xx) (min, max) (xx.xx, xx.xx) Performance status at time of initiation of CRT Xx n Xx Missing Xx Mean (SD) xx.x (xx.xx) Median xx.x (min, max) xx.x	Mean (SD)	xx.x (xx.xx)
Number of cycles (Concurrent) Xx n Xx Missing Xx Mean (SD) xx.x (xx.xx) Median xx.x (min, max) (xx.xx, xx.xx) Tumor response assessment done on imaging (days) Xx n Xx Missing Xx Median (SD) xx.x (xx.xx) Median xx.x (min, max) (xx.xx, xx.xx) Performance status at time of initiation of CRT Xx Missing Xx Mean (SD) xx.x (xx.xx) Median xx.x (min, max) (xx.xx, xx.xx)	Median	xx.x
n Xx Missing Xx Mean (SD) xx.x (xx.xx) Median xx.x (min, max) (xx.xx, xx.xx) Tumor response assessment done on imaging (days) Xx n Xx Missing Xx Mean (SD) xx.x (xx.xx) Median xx.x (min, max) (xx.xx, xx.xx) Performance status at time of initiation of CRT Xx Missing Xx Mean (SD) xx.x (xx.xx) Median xx.x (min, max) (xx.xx, xx.xx) Median xx.x (min, max) (xx.xx, xx.xx)	(min, max)	(xx.xx, xx.xx)
Missing Xx Mean (SD) xx.x (xx.xx) Median xx.x (min, max) (xx.xx, xx.xx) Tumor response assessment done on imaging (days) Xx n Xx Missing Xx Mean (SD) xx.x (xx.xx) Median xx.x (min, max) (xx.xx, xx.xx) Performance status at time of initiation of CRT Xx Missing Xx Mean (SD) xx.x (xx.xx) Median xx.x (min, max) (xx.xx, xx.xx) Median xx.x (min, max) (xx.xx, xx.xx)	Number of cycles (Concurrent)	
Mean (SD) xx.x (xx.xx) Median xx.x (min, max) (xx.xx, xx.xx) Tumor response assessment done on imaging (days) Xx n Xx Missing Xx Mean (SD) xx.x (xx.xx) Median xx.x (min, max) (xx.xx, xx.xx) Performance status at time of initiation of CRT Xx Missing Xx Mean (SD) xx.x (xx.xx) Median xx.x (min, max) (xx.xx, xx.xx)	n	Xx
Median (min, max) xx.x Tumor response assessment done on imaging (days) Xx N Xx Missing Xx Mean (SD) xx.x (xx.xx) Median xx.x (xx.xx) (min, max) (xx.xx, xx.xx) Performance status at time of initiation of CRT Xx Nissing Xx Mean (SD) xx.x (xx.xx) Median xx.x (min, max) (xx.xx, xx.xx)	Missing	Xx
(min, max) (xx.xx, xx.xx) Tumor response assessment done on imaging (days) Xx n Xx Missing Xx Mean (SD) xx.x (xx.xx) Median xx.x (min, max) (xx.xx, xx.xx) Performance status at time of initiation of CRT Xx n Xx Missing Xx Mean (SD) xx.x (xx.xx) Median xx.x (min, max) (xx.xx, xx.xx)	Mean (SD)	xx.x (xx.xx)
Tumor response assessment done on imaging (days) Xx N Xx Missing Xx Median xx.x (min, max) (xx.xx, xx.xx) Performance status at time of initiation of CRT Xx N Xx Missing Xx Mean (SD) xx.x Median xx.x (min, max) (xx.xx, xx.xx)	Median	xx.x
n Xx Missing Xx Mean (SD) xx.x (xx.xx) Median xx.x (min, max) (xx.xx, xx.xx) Performance status at time of initiation of CRT Xx n Xx Missing Xx Mean (SD) xx.x (xx.xx) Median xx.x (min, max) (xx.xx, xx.xx)	(min, max)	(xx.xx, xx.xx)
Missing Xx Mean (SD) xx.x (xx.xx) Median xx.x (min, max) (xx.xx, xx.xx) Performance status at time of initiation of CRT Xx n Xx Missing Xx Mean (SD) xx.x (xx.xx) Median xx.x (min, max) (xx.xx, xx.xx)	Tumor response assessment done on imaging (days)	
Mean (SD) xx.x (xx.xx) Median xx.x (min, max) (xx.xx, xx.xx) Performance status at time of initiation of CRT Xx n Xx Missing Xx Mean (SD) xx.x (xx.xx) Median xx.x (min, max) (xx.xx, xx.xx)	n	Xx
Median xx.x (min, max) (xx.xx, xx.xx) Performance status at time of initiation of CRT Xx n Xx Missing Xx Mean (SD) xx.x (xx.xx) Median xx.x (min, max) (xx.xx, xx.xx)	Missing	Xx
(min, max) (xx.xx, xx.xx) Performance status at time of initiation of CRT Xx n Xx Missing Xx Mean (SD) xx.x (xx.xx) Median xx.x (min, max) (xx.xx, xx.xx)	• •	xx.x (xx.xx)
Performance status at time of initiation of CRT Xx n Xx Missing Xx Mean (SD) xx.x (xx.xx) Median xx.x (min, max) (xx.xx, xx.xx)	Median	xx.x
n Xx Missing Xx Mean (SD) xx.x (xx.xx) Median xx.x (min, max) (xx.xx, xx.xx)	(min, max)	(xx.xx, xx.xx)
Missing Xx Mean (SD) xx.x (xx.xx) Median xx.x (min, max) (xx.xx, xx.xx)	Performance status at time of initiation of CRT	
Mean (SD) xx.x (xx.xx) Median xx.x (min, max) (xx.xx, xx.xx)	n	Xx
Median xx.x (min, max) (xx.xx, xx.xx)	Missing	Xx
(min, max) (xx.xx, xx.xx)	, ,	xx.x (xx.xx)
	Median	xx.x
		(xx.xx, xx.xx)

- The Capital "N" in the column header represents the total number Enrolled Analysis Set.
- The small "n" represents the total number of patients in the row category.
- Percentages are based on total number of Enrolled Analysis Set.
- SD = Standard Deviation, min=minimum, max=maximum
- Source: Listing 16.1.9.1 and Listing 16.1.9.2

Document Title:	Document ID:	BP04-01
Statistical Analysis Dlan	Version Number:	3.1 25-Nov-2021
Statistical Analysis Plan	Effective Date:	

Table 14.1.8 Summary of WHO Performance Status (Safety Analysis Set)

	N = xx
Visit 1	
WHO Performance Grade	
0 = Fully active, able to carry on all pre-disease performance without restriction	xx (xx.xx)
1 = Restricted in physically strenuous activity but ambulatory and able to carry out work of a light or sedentary nature	xx (xx.xx)
2 = Restricted in physically strenuous activity but ambulatory and able to carry out work of a light or sedentary nature, e.g., light housework, office work	xx (xx.xx)
3 = Capable of only limited self-care, confined to bed or chair more than 50% of waking hours	xx (xx.xx)
4 = Completely disabled. Cannot carry on any self-care. Totally confined to bed or chair	xx (xx.xx)
5 = Dead	xx (xx.xx)
Visit x	
WHO Performance Grade	
0 = Fully active, able to carry on all pre-disease performance without restriction	xx (xx.xx)
1 = Restricted in physically strenuous activity but ambulatory and able to carry out work of a light or sedentary nature	xx (xx.xx)
2 = Restricted in physically strenuous activity but ambulatory and able to carry out work of a light or sedentary nature, e.g., light housework, office work	xx (xx.xx)
3 = Capable of only limited self-care, confined to bed or chair more than 50% of waking hours	xx (xx.xx)
